9.1 Determination of Sample Size and Power Estimate

In protocol version 2.1 the primary analysis was amended to determine if FET PET can differentiate between benign treatment-related changes (TRC) and recurrent glioma in comparison to a composite standard of truth (CSOT) that includes pathology and other clinical information, evaluated using estimates of sensitivity and specificity. With the amendment of the primary endpoints, the study sample size calculations were updated.

1. [Section 9.1.1](#) describes the sample size calculation for analysis of the co-primary endpoints of sensitivity and specificity under protocol version 2.1.
2. [Section 9.1.2](#) describes the sample size calculation based on the initial planned analysis of misclassification rate, prior to protocol version 2.1.

9.1.1 Amended Sample Size Calculation - Protocol Version 2.1

For protocol version 2.1, the sample size was determined based on separate estimates of sample size for each of the co-primary endpoints (sensitivity and specificity). The greater of the two estimates was taken as the required sample size of the study. For each endpoint, the calculation computed the probability of whether the lower limit of a 95% Wilson confidence interval for a binomial proportion was greater than the null proportions of 0.70 and 0.68 for sensitivity and specificity, respectively. Other assumptions include prevalence of glioma recurrence=0.50, observed sensitivity=0.81, and observed specificity=0.79. The sample size for each estimate was set as the smallest positive integer that provides power ≥ 0.80 . Given these assumptions, the estimated sample size is N=118.

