2. **Recurrent high-grade glioma (Grade 3 and 4):** Based on prior data from UCSF, we anticipated that 70% of patients would have recurrent tumor at the time of imaging (12). Using this same paper as an estimate of misclassification rate using MRI for the characterization of recurrent tumor, resulted in a sensitivity of 82%, specificity of 76%, prevalence of 70% and a misclassification rate of 19.8%. For FET PET, the first paper to publish the sensitivity and specificity of FET PET was Rachinger et al in 2005; they reported a sensitivity, specificity and misclassification rate of 100%, 93% and 2% respectively (45 patients with a prevalence of 69%) (13). A subsequent paper published in 31 patients, 26 of whom had recurrent tumor, had a sensitivity of 100% and a specificity of 84%, resulting in a misclassification rate of 2.6% (14). A third paper looked at the ability to characterize pseudoprogression after radiochemotherapy all of whom had an enhancing lesion on MRI, demonstrated a sensitivity, specificity and misclassification rate of 100%, 91% and 5% respectively (6). No meta-analysis exists for estimating the accuracy of FET PET, and therefore we have selected 5% as a reasonable goal misclassification rate. Our null hypothesis was that there is no difference between MRI and FET PET misclassification rates (19.8% for MRI and 5% for FET PET). For our sample size analysis, we used a binomial test for proportions. Therefore, 27 patients needed to be imaged with pathologic correlation to demonstrate the difference with a significance level of 0.05 with a power of 80%, and using a one-sided t-test. Our null hypothesis was that there is no difference between MRI and FET PET misclassification rates (H_{null} : MRI_misclass = FET PET misclass = 19.8%). The alternative hypothesis was that the FET PET misclassification rate is lower (H_{alt} : FET PET misclass < MRI_misclass = 19.8%). We estimated that 40% of patients would have pathology as a correlate, and we would replace all patients who did not have pathology within four weeks of imaging to fill our primary endpoint. Therefore the total patient population in population 1 with high grade gliomas was 68 patients.

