- 3. Recurrent low-grade glioma (Grade 1 and 2):** We included this population as a secondary endpoint in order to gain information on the role of FET PET in the characterization of low-grade gliomas. We aimed to image 20 patients as part of this cohort to obtain preliminary information about the role of FET PET in this population.

Population 2: For population 2 we selected a misclassification rate for the characterization of tumor as either low or high grade. Most of the data on the literature for the effectiveness of conventional imaging (MRI) for the classification of disease is reported as sensitivity and specificities; the best meta-analysis available suggests that MR spectroscopy has a sensitivity of 75% and a specificity of 70% (15). In this meta-analysis of 25 studies, there were 427 low-grade and 802 high-grade tumors, resulting in a prevalence of 65% for high-grade tumors. Assuming a prevalence of 65%, this would imply a misclassification rate of 27% for conventional imaging. Using a recent FET PET article that demonstrated a sensitivity and specificity of 100% and 73% respectively for the characterization of low-grade and high-grade gliomas with a prevalence of 52%, we estimated a misclassification rate of roughly 13% for FET PET (16). Therefore, our target misclassification rate was 13%. Our null hypothesis was that there is no difference between MRI and FET PET misclassification rates (27% for MRI and 13% for FET PET). For our sample size analysis, we used a binomial test for proportions. Therefore, 49 patients needed to be imaged with pathologic correlation to demonstrate the difference with a significance level of 0.05 with a power of 80%, using a one-sided test. Our null hypothesis is that there is no difference between MRI and FET PET misclassification rates (H_{null} : $\text{MRI_misclass} = \text{FET PET misclass} = 27\%$). The alternative hypothesis is that the FET PET misclassification rate is lower (H_{alt} : $\text{FET PET misclass} < \text{MRI_misclass} = 27\%$).

We estimated that 50 patients with intracranial neoplasms would be enrolled each year, and we estimated that we would enroll 199 patients over the four years of the study.

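### The 0.50 recurrence prevalence behind N=118 has no source and is in tension with the plan's own 70% for high-grade glioma; any higher prevalence takes further power from specificity, which is already short

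*Combined protocol and SAP*

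**What the plan says.** Section 9.1.1 takes the endpoints one at a time, sensitivity first, and defines power as the chance of this event: "lower limit of a 95% Wilson confidence interval for a binomial proportion was greater than the null proportions of 0.70 and 0.68". The remaining inputs are: "Other assumptions include prevalence of glioma recurrence=0.50, observed sensitivity=0.81, and observed specificity=0.79". On the target it states: "The sample size for each estimate was set as the smallest positive integer that provides power" of at least 0.80. The two results are combined by taking the larger ("The greater of the two estimates was taken as the required sample size of the study"), and the section ends: "Given these assumptions, the estimated sample size is N=118".

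Section 9.1.2 keeps the calculation used before protocol version 2.1, when the endpoint was misclassification rate. For high-grade glioma, citing prior data from the trial's own centre, it says "we anticipated that 70% of patients would have recurrent tumor at the time of imaging". It also cites two glioma series with prevalences of 69% and 26/31 (84%). Its planned numbers are: "Therefore the total patient population in population 1 with high grade gliomas was 68 patients", and for low-grade glioma "We aimed to image 20 patients as part of this cohort". It gives no low-grade prevalence.

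Section 9.2.1 limits the efficacy dataset to gliomas. Section 9.2.2 requires both lower bounds to pass for the same two of three, evidently readers.

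**The concern.** Specificity is estimated only in patients whom the composite standard calls treatment-related change. A prevalence of 0.50 splits 118 into 59 and 59, which makes the two endpoints look about equally powered. If the true share with recurrence is higher, the truth-negative group shrinks and specificity becomes the clear weak point. Success needs both endpoints, so the weaker one governs.

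Section 9.1 explains why the endpoint changed in version 2.1. It does not say why 0.50 was used when a 70% expectation for most of the planned gliomas stands in the next subsection. A sponsor who corrected N but left the prevalence alone would still overstate specificity power.

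**Working it through.** **Inputs.** From 9.1.1: null values 0.70 and 0.68, assumed true values 0.81 and 0.79, prevalence 0.50, two-sided 95% Wilson interval (z = 1.96), target power 0.80, N = 118. From 9.1.2: 70% in high-grade, 68 high-grade, 20 low-grade.

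**Formula.** With x correct reads among n patients and p = x/n, the Wilson lower limit is L = [p + z²/(2n) − z·√(p(1−p)/n + z²/(4n²))] / (1 + z²/n). Power is P(X ≥ c), where c is the smallest x with L above the null and X ~ Binomial(n, assumed true value).

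**Step 1: the plan's own figure, at prevalence 0.50.**
- Specificity, n = 59: x = 47 gives L = 0.677 and x = 48 gives 0.696, so c = 48. Power is 0.399.
- Sensitivity, n = 59: c = 49, power 0.420.
- Smallest n with power of at least 0.80: 120 for sensitivity (c = 94, power 0.807) and 126 for specificity (c = 96, power 0.813).
- Total N: 120/0.50 = 240 and 126/0.50 = 252. The larger is 252.

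The stated 118 is therefore not reproduced. One-sided limits and Wald, Clopper-Pearson, Agresti-Coull, Jeffreys and continuity-corrected intervals were also tried. None gives 59 per class at 80% power; the most lenient, one-sided Wald, needs 77 and 87. The figure 118 is close to a single-class requirement, as if it had not been divided by prevalence, but the documents do not say so.

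**Step 2: prevalence implied by Section 9.1.2.** The 68 high-grade patients contribute 0.70 × 68 = 47.6 recurrences.
- No low-grade recurrence: 47.6/88 = 0.54.
- Half of low-grade: (47.6 + 10)/88 = 0.65.
- Low-grade also 70%: 0.70.
- All low-grade: (47.6 + 20)/88 = 0.77.

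**Step 3: power at N = 118 over that range.** Exact power moves in a sawtooth with n (54 truth-negatives give 0.401 and 59 give 0.399), so the table averages over a truth-negative count distributed Binomial(118, 1 − prevalence), and likewise for truth-positives. Figures are for one reader.

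| Prevalence | Expected truth-positives / truth-negatives | Sensitivity power | Specificity power |
|---|---|---|---|
| 0.50 | 59 / 59 | 0.46 | 0.45 |
| 0.54 | 64 / 54 | 0.50 | 0.42 |
| 0.65 | 77 / 41 | 0.57 | 0.33 |
| 0.70 | 83 / 35 | 0.60 | 0.28 |
| 0.77 | 91 / 27 | 0.65 | 0.21 |

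With exactly 35 truth-negatives, specificity power is 0.227.

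**Step 4: isolating prevalence.** As an illustration only, take N = 252, the size that meets the plan's rule at 0.50. Averaged specificity power is 0.78 at prevalence 0.50, 0.75 at 0.54, 0.62 at 0.65 and 0.55 at 0.70. Sensitivity power rises from 0.80 to 0.92 between 0.50 and 0.70. The prevalence loss therefore remains after N is corrected, and it falls only on specificity.

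**The case against.** The strongest reply is that the 0.54 to 0.77 range borrows a mix that no longer applies. The 68:20 split totals 88 gliomas and belongs to a superseded calculation. The current one needs 118, and no section gives their grade mix. If 68 were high-grade at 70% and the other 50 low-grade, overall prevalence would be 0.50 at a low-grade rate of (59 − 47.6)/50 = 23%. This stands. A reader might infer from 68:20 that 0.50 cannot occur, since the 88 would need a low-grade rate of (44 − 47.6)/20 = −18%. The documents do not support that inference for 118 patients of unstated mix.

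Second, the 70% was set for high-grade patients in a calculation that required pathologic correlation, expected in 40% of them. The current standard is composite (Section 8.1.2.1) and also classifies patients without tissue. Some of its rules raise prevalence (clinical decline or death without imaging counts as recurrence) and some lower it (new lesions elsewhere do not count). The direction is not settled. This also stands.

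Third, one further glioma series in 9.1.2 (sensitivity 100%, specificity 91%, misclassification 5%) implies a prevalence near 1 − 0.05/0.09 = 0.44, so 0.50 may be defensible. But the plan does not make that argument, and its two explicit series (69% and 84%) point the other way.

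Fourth, the loss is small at the low end: 0.45 to 0.42 at prevalence 0.54, and none with fixed counts of 59 and 54. That is correct; the loss becomes material from the middle of the range upward.

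**Conclusion.** The point holds as an unsupported planning assumption with a one-sided consequence. The 0.50 has no stated source and is in tension with the plan's 70% for high-grade glioma and with the only grade mix it gives.

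The larger defect is separate: N = 118 gives about 0.40 to 0.45 specificity power even at 0.50. A reader might blame prevalence for the whole gap to 0.80, but most of the gap is there before prevalence changes. Prevalence then takes specificity power to about 0.42, 0.33 or 0.28 at 0.54, 0.65 or 0.70. On these inputs specificity is marginally the weaker endpoint at 0.50 and clearly the limiting one above it.

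A reader might also conclude that the trial must enrol 126/0.30 = 420. That would apply the high-grade 70% to every glioma, which the documents do not establish.

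The figures rest on the plan's assumed true values of 0.81 and 0.79, one reader, exact binomial power and, for the prevalence range, the 68:20 mix with 70% in high-grade.

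**What to change.** In Section 9.1.1:

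- Give a source for 0.50 under the composite standard, or replace it with a blend that states the high-grade rate, the low-grade rate and the expected grade mix of the 118.
- Replace the single claim of at least 0.80 power with separate sensitivity and specificity power at the planned N. Show expected truth-positive and truth-negative counts over prevalences of about 0.50 to 0.77, and say whether class sizes are fixed or random.
- Show the calculation behind 118 and say whether it is a total or a per-class count.
- State that specificity is the limiting endpoint when prevalence exceeds 0.50.

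This costs recalculation and rewording of one section. It asks for no change to enrolment, procedures or success thresholds. The downside is a visibly less favourable specificity power.

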| Rationale for Study | FET accumulates in malignant cells within intracranial neoplasms and can be used to detect recurrent disease and characterize grade of glial neoplasms. |
| Primary Objective | To determine if FET PET can differentiate between benign treatment-related changes (TRC) and recurrent glioma in comparison to a composite standard of truth (CSOT) that includes pathology and other clinical information, evaluated using estimates of sensitivity and specificity. |
| Secondary Objectives | 
 1) To determine if FET PET can differentiate between benign TRC and recurrent glioma in comparison to a histopathological standard of truth. 2) To determine if FET PET can differentiate between benign TRC and recurrent glioma in comparison to a CSOT evaluated using estimates other than subject-based sensitivity and specificity. 3) To assess the safety of FET PET, as determined by treatment emergent adverse events (TEAEs) within 48 hours of FET administration. 4) To describe the inter-reader variability between 3 independent blinded readers of FET PET images in their assessments of benign TRC versus recurrent glioma. 5) To describe intra-reader variability between 3 independent blinded readers of FET PET images in their assessments of benign TRC versus recurrent glioma. |

| | |
|------------------------|--|
| Exploratory Objectives | 
 1) To assess relationships between serial FET PET and clinical outcome (benign TRC and recurrence) in patients with recurrent metastatic lesions, recurrent high grade gliomas and recurrent low grade gliomas. 2) To determine if MRI can differentiate between benign treatment-related changes and recurrence. 3) To describe the distribution of the standardized uptake value (SUV) and tumor-to-background ratio (TBR) for observed lesions. 4) To determine if FET PET can differentiate between benign TRC and recurrent metastatic lesions. 5) To determine if FET PET can accurately differentiate between low-grade and high-grade gliomas in population 2. |
| Study Design | This is a prospective, Phase 2, single center, open-label study in patients with intracranial neoplasms. There is a provision of Stopping Rules for the Pediatric patient population. |
| Number of patients | 199 patients, enrolled over four years. 150 patients will be enrolled in patient population 1 and 49 patients will be enrolled in patient population 2. |

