8.2 Efficacy Analysis Variables

8.2.1 General Efficacy Analyses

Sensitivity, specificity, positive predictive value, negative predictive value, accuracy, and misclassification rate will be presented per subject by individual reader. There will also be a majority rule summary of the three readers' results where the calculations are based on the FET PET result (positive or negative) agreed to by the majority of the readers (2 or 3 readers). Wilson's binomial (score) 95% confidence intervals will be presented for each reader and for majority rule result.

Standardized uptake value (SUV) and tumor-to-background ratio (TBR) will be summarized per lesion for each reader. Individual readers' results will be presented in a listing.

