For our sample size analysis, we used a binomial test for proportions. Assuming a misclassification rate of 35% for conventional MRI and 10% for FET PET, 34 patients needed to be imaged with pathologic correlation to demonstrate the difference with a significance level of 0.01 with a power of 90%, and a one-sided test. Our null hypothesis was that there is no difference between MRI and FET PET misclassification rates (H_{null} : MRI_misclass = FET PET misclass = 35%). The alternative hypothesis was that the FET PET misclassification rate is lower (H_{alt} : FET PET misclass < MRI_misclass = 35%). We estimated that 55% of patients would have pathology as a correlate, and we would replace all patients who did not have pathology within four weeks of imaging to fill our primary endpoint. Therefore the total patient population in population 1 with metastatic lesions was 62 patients.

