9.2.2 Analysis of Primary Endpoints

Sensitivity, specificity, and 95% confidence interval (CI) will be calculated per the formulas in [Section 8.2.2](#), using the definitions of TP, FP, TN, and FN from [Section 8.1.3](#) and the CSOT. This will be done on a subject-specific basis based on the blinded readers' overall assessment.

The lower boundary of the 95% confidence interval for sensitivity will be compared to the threshold of 0.70 and for specificity it will be compared to 0.68.

Overall study success criteria: the lower bounds of the 95% CIs of the primary analysis of sensitivity and specificity must be greater than or equal to 0.70 and 0.68 respectively for at least the same 2 out of 3.

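### N=118 does not give the stated power of at least 0.80 per co-primary endpoint: on the plan's own inputs it gives about 0.40 to 0.46, and about 260 gliomas would be needed

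*Combined protocol and SAP*

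**What the plan says.** Section 9.1.1 of the combined protocol and SAP gives a complete recipe. Each co-primary endpoint is sized on the probability that "the lower limit of a 95% Wilson confidence interval for a binomial proportion was greater than the null proportions of 0.70 and 0.68"; the first null applies to sensitivity and the second to specificity. The assumed values are prevalence 0.50, sensitivity 0.81 and specificity 0.79. "The sample size for each estimate was set as the smallest positive integer that provides power" of at least 0.80, and the larger of the two results becomes the study size. The section ends: "Given these assumptions, the estimated sample size is N=118".

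Section 8.2.2 defines sensitivity as TP/(TP+FN) and specificity as TN/(TN+FP), so each endpoint has its own denominator. Section 8.2.1 says: "Wilson's binomial (score) 95% confidence intervals will be presented for each reader and for majority rule result".

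Section 9.2.2 sets the success rule: the two lower bounds "must be greater than or equal to 0.70 and 0.68 respectively for at least the same 2 out of 3". Section 9.2.1 restricts the efficacy set to glioma patients. On enrolment, the Abstract says: "150 patients will be enrolled in patient population 1 and 49 patients will be enrolled in patient population 2".

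**The concern.** A total of 118 at prevalence 0.50 leaves about 59 subjects for each endpoint. The margins to be shown are 0.81 against 0.70 and 0.79 against 0.68, a gap of 0.11 in each case. A 95% interval on 59 subjects is too wide to resolve a gap of that size reliably.

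Section 1.1 says the data are meant to support an NDA. If the stated power is wrong, a tracer that performs exactly as assumed would probably fail the primary analysis, and the failure could be read as a deficiency of the tracer. The sizing also treats one endpoint at a time, whereas success requires both together.

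**Working it through.** **Inputs.** Nulls 0.70 and 0.68, assumed values 0.81 and 0.79, prevalence 0.50 and target power 0.80 come from Section 9.1.1. The denominators come from Section 8.2.2. The 95% interval is taken as two-sided, z = 1.96.

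**Formulas.** With p = x/n, the Wilson lower limit is

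L(x, n) = [p + z²/(2n) − z·√(p(1−p)/n + z²/(4n²))] / (1 + z²/n).

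Let c be the smallest x with L(x, n) at or above the null. Power is P(X ≥ c) for X ~ Binomial(n, assumed value). Using a strict inequality (Section 9.1.1) or a non-strict one (Section 9.2.2) does not change the conclusion.

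**Step 1: try to reproduce 118.** Following the recipe, power first reaches 0.80 at these class sizes:

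- Sensitivity: n = 120 recurrent subjects (c = 94, power 0.807). Total 120/0.50 = 240.
- Specificity: n = 126 subjects with treatment-related change (c = 96, power 0.813). Total 126/0.50 = 252.

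The greater of the two is 252, so 118 is not reproduced.

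**Step 2: power that 118 patients give.**

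| Reading of N=118 | Sensitivity | Specificity |
|---|---|---|
| 59 per class (c = 49 and 48) | 0.420 | 0.399 |
| Random split, Binomial(118, 0.5) | 0.465 | 0.446 |
| 59 per class, one-sided 95% Wilson limit | 0.552 | 0.526 |
| 118 in each class, prevalence ignored (c = 93 and 91) | 0.769 | 0.735 |

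At 59 per class, Wald, Agresti-Coull, Clopper-Pearson, Jeffreys and continuity-corrected Wilson limits were also tried. At one-sided 0.05 or stricter, none exceeds 0.68. For 80% power at 59 per class the true values would have to be about 0.86 and 0.845.

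**Step 3: the trial that observes its own assumptions.** The nearest counts are 48/59 = 0.814 and 47/59 = 0.797. For 48/59:

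L = [0.8136 + 0.0326 − 1.96·√(0.002571 + 0.000276)] / 1.0651 = 0.696, below 0.70.

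For 47/59, L = 0.677, below 0.68. Both endpoints miss.

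**Step 4: the size that does work.** Exact power moves in a sawtooth as n grows. With 252 patients split 126/126, specificity has 0.813 but sensitivity only 0.793. The smallest equal split with both at 0.80 or more is 130/130 (0.804 and 0.818), total 260. Averaging over a random split gives 250 for sensitivity and 262 for specificity.

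**Step 5: the full success rule.** In one reader the two endpoints use different subjects, so at 59/59 the chance of meeting both is 0.420 × 0.399 = 0.168. Over a random split it is 0.206. Section 9.2.2 then asks for the same 2 of 3, read here as readers. For independent readers with q = 0.168, the chance is 3q²(1−q) + q³ = 0.075. For correlated readers, a shared-subject latent normal model with equal accuracy in each reader was simulated (40,000 runs):

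| Assumed latent correlation | 0 | 0.3 | 0.5 | 0.7 | 0.9 | 1 |
|---|---|---|---|---|---|---|
| Fixed 59/59 split | 0.07 | 0.09 | 0.11 | 0.12 | 0.14 | 0.17 |
| Random split | 0.11 | 0.13 | 0.14 | 0.16 | 0.18 | 0.21 |

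Even at 130 per class, both endpoints in one reader has probability 0.804 × 0.818 = 0.658. Reaching 0.80 jointly in one reader takes about 316 patients.

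**The case against.** The best defence of 118 is that it was meant per class. Section 9.1.1 does not support this: it lists prevalence as an input and presents the result as the size of the study. The reading would not help either, since 118 per class still falls below 0.80 on both endpoints. The figure does lie close to some per-class results by other methods (118.6 for sensitivity by an arcsine formula; 118 for specificity with a Jeffreys interval). That suggests the division by prevalence was left out, but this is an inference about origin, and the plan names neither method.

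Four stronger readings are tempting, and the documents do not support them as findings.

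- **252 is the right total.** It follows the plan's greater-of-the-two rule, but at 126/126 it leaves sensitivity at 0.793.
- **The success rule has a known probability, such as 10 to 15%.** The documents give no reader correlation; Section 9.2.3 only plans to estimate agreement. The rule also ends without a noun, so readers is an inference. Only a range can be stated.
- **Prevalence is really 70%.** Section 9.1.2 does say "we anticipated that 70% of patients would have recurrent tumor at the time of imaging", but that concerns high-grade glioma only and belongs to the calculation used before version 2.1. The current assumption for all glioma is 0.50. The higher figure is a scenario, not a contradiction.
- **Enrolment cannot reach 118 gliomas.** The cohort targets in Section 9.1.2 are 62 metastatic ("Therefore the total patient population in population 1 with metastatic lesions was 62 patients"), 68 high-grade and 20 low-grade, which leaves 68 + 20 = 88 gliomas. Those targets are superseded and were inflated for missing pathology. The current text sets 150 for Population 1 with no glioma quota, so 118 gliomas could fit. What stands is narrower: no minimum number of Population 1 gliomas is stated.

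A headline of 40% alone would also be a little harsh. Recurrence status is unknown at enrolment, and averaging over the split raises power to 0.465 and 0.446.

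**Conclusion.** The power statement in Section 9.1.1 is wrong on its own inputs. N=118 gives about 0.40 to 0.46 per co-primary endpoint, roughly half of what is claimed, and about 260 gliomas (130 per class) are needed for 0.80 on each. This conclusion rests only on figures in the plan and on the class-specific denominators, and no interval method tried at the 95% level rescues it.

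The chance of meeting the full success rule is about 0.07 to 0.17 with a fixed split, or 0.11 to 0.21 with a random split, across reader correlations from 0 to 1. That range depends on reading the rule as 2 of 3 readers, on equal reader accuracy and on the latent model. Every value in it is far below 0.80.

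**What to change.** Restate Section 9.1.1 as follows.

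1. Report that N=118, about 59 per class at prevalence 0.50, gives power of about 0.42 and 0.40 (0.46 and 0.45 over a random split) for sensitivity and specificity.
2. State that power first reaches 0.80 at 120 recurrent and 126 treatment-related-change subjects, and that 260 gliomas (130 per class) is the smallest equal split with both at 0.80 or more.
3. Give the probability of meeting the complete rule in Section 9.2.2 as a range, labelled with the assumed reader correlation, and say there that the 2 out of 3 refers to readers, if that is meant.
4. Optionally show a higher-prevalence scenario. At 70%, 118 splits about 83/35 and power is 0.59 for sensitivity and 0.23 for specificity.

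It would also help to state how many of the 150 Population 1 patients are expected to be gliomas.

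The cost is wording and a less favourable stated power. No patients are added. The change discloses the low power but does not restore it; restoring it would need more gliomas.
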